1. PROTOCOL SYNOPSIS

PROTOCOL TITLE	An Open Label Extension, Multi-Center, Study to Evaluate the Safety of SD-101 Cream in Subjects with Epidermolysis Bullosa
PROTOCOL No.	SD-004
VERSION No.	4
SPONSOR	Scioderm, INC An Amicus Therapeutics Company [name]
INVESTIGATIONAL PRODUCT	SD-101 cream administration containing 6% allantoin
PHASE OF DEVELOPMENT	Open Label Extension
INDICATION AND RATIONALE	The aim is to assess the continued safety of topical use of SD-101 cream containing 6% allantoin in subjects with Epidermolysis Bullosa.
STUDY DESIGN	
This is an open label extension, multi-center, study to assess the continued safety of topically applied SD-101 cream containing 6% allantoin in subjects with Simplex, Recessive Dystrophic, and Junctional non-Herlitz Epidermolysis Bullosa.
 
SD-101 cream containing 6% allantoin will be applied topically, once a day to the entire body for the duration of the study. Subjects who successfully complete the entire SD-003 study will have the option to roll over into the SD-004 study. The baseline visit 1 will occur at the final visit date for SD-003. The Body Surface Area (BSA) coverage of blisters and lesions assessment made at the final SD-003 study visit will be used as the baseline information at visit 1 for the SD-004 study. The subject will return to the study site once every 3 months for visit 2 (14 days \pm7 days from baseline) through visit 14 (1080 days \pm7 days from baseline) to have Body Surface Area (BSA) assessed. Body Surface Area will be assessed at all subsequent scheduled study center visits. Scheduled study center visits occur every 6 months after visit 14 (visits 16, 18, 20, etc.). After completion of visit 14, the next subject visit (visit 15) will be a phone call from the site to the patient. Telephone visits will occur every

6 months thereafter (visits 17, 19, 21, etc.) and include assessment of adverse events and concomitant medications only. At the Investigator's discretion, the subject may be asked to complete a study center visit in place of a phone call visit. If a study center visit is requested, no additional assessments for that visit (other than collection of information on adverse events and concomitant medications) will be required. Urine pregnancy tests will be performed at visit 4 and every 6 months up to and including the final study visit.

STUDY OBJECTIVES

Primary Objective

The primary objective is to demonstrate in subjects with Simplex, Recessive Dystrophic, and Junctional non-Herlitz Epidermolysis Bullosa, the continued safety of SD-101 cream containing 6% allantoin.

Secondary Objective

The secondary objective is to continue to assess the change in Body Surface Area (BSA) of blisters or lesions.

PLANNED SAMPLE SIZE

Approximately 48 subjects are expected to roll over from Study SD-003 into this open-label extension.

PATIENT POPULATION

Inclusion Criteria

1. Informed Consent form signed by the subject or subject's legal representative; if the subject is under the age of 18 but capable of providing assent, signed assent from the subject.
2. Subject (or caretaker) must be willing to comply with all protocol requirements.
3. Subjects must successfully complete the SD-003 study.

PATIENT POPULATION

Exclusion Criteria

1. Subjects who do not meet the entry criteria outlined above.
2. Pregnancy or breastfeeding during the study. (A urine pregnancy test will be performed at the final visit for SD-003 for female subjects of childbearing potential).
3. Females of childbearing potential who are not abstinent and not practicing a medically acceptable method of contraception.

FORMULATION/DOSE	SD-101 cream will be applied topically, once a day to the entire body for the duration of the study. Application will consist of SD-101 containing 6% allantoin.
ROUTE OF ADMINISTRATION	Topical administration of SD-101 dermal cream containing 6% allantoin
DURATION/FREQUENCY OF TREATMENT	Topical application of SD-101 containing 6% allantoin once daily for the duration of the study. The planned duration of the treatment will vary among subjects and will continue until commercialization or availability of an alternate access approach or study termination by the Sponsor (see Section 8.4 and Section 13 for details).
SAFETY ASSESSMENTS	The safety of SD-101 containing 6% allantoin will be assessed by monitoring tolerability at the application sites, adverse events, and periodic physical examinations.
STATISTICAL CONSIDERATIONS	This study is an open label extension of SD-003 and will include those patients completing that study and wishing to receive SD-101 (allantoin 6%). In general, results will be summarized using descriptive statistics.

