8.4. Withdrawal Criteria/Study Discontinuation

Subjects may withdraw from the study at any time without stating a reason and without prejudice to further treatment. The Investigator may withdraw a subject from the study and discontinue study treatment and assessments at any time due to safety concerns. Full skin examination will be performed at each scheduled study center visit. If SD-101 causes any significant rash that has not occurred previously in the subject, the Investigator should consider discontinuing the subject. In addition, if lesions appear to significantly worsen above the normal cycle seen in the patient, with use of SD-101, the Investigator should consider discontinuing the subject.

Early discontinuation of any subject who has given informed consent / assent to participate will be recorded including the reason for discontinuation. The primary reason for a subject withdrawing prematurely will be selected from the following standard categories of early discontinuations.

1. Adverse Event (Adverse Reaction): Clinical events occurred that are reported that in the medical judgment of the Investigator are grounds for discontinuation in the best interests of the subject.
2. Withdrawal of Consent: The subject desired to withdraw from further participation in the study. The subject is not obligated to provide any reason for withdrawal of consent, but where a reason is given this will be recorded on the eCRF.
3. Protocol Violation: The subject failed to adhere to the protocol requirements, at the Investigator's discretion.

4. Lost to Follow-Up: The subject stopped coming for visits and study personnel were unable to contact the subject.
5. Other: The subject was terminated for a reason other than those listed above, such as, termination of study by Sponsor.

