9.3. Study Design

This is an open label extension, multi-center study to assess the continued safety of SD-101 cream (containing 6% allantoin) in treating subjects with Simplex, Recessive Dystrophic, and Junctional non-Herlitz Epidermolysis Bullosa.

SD-101 cream (containing 6% allantoin) will be applied topically, once a day to the entire body for the duration of the study. Subjects who successfully complete the SD-003 study will be eligible to roll over into the SD-004 study. The baseline visit 1 will occur at the final visit date for SD-003. The BSA assessment from the final SD-003 study will be used as the baseline information at visit 1 for the SD-004 study. The subject will return to the study site once every 3 months for visit 2 (14 days \pm 7 days from baseline) through visit 14 (1080 days \pm 7 days from baseline) to have BSA assessed. Body Surface Area will be assessed at all subsequent scheduled study center visits. Scheduled study center visits occur every 6 months after visit 14 (visits 16, 18, 20, etc.). After completion of visit 14, the next subject visit (visit 15) will be a phone call from the site to the patient. Telephone visits will occur every 6 months thereafter (visits 17, 19, 21, etc.) and include assessment of adverse events and concomitant medications only. At the Investigator's discretion, the subject may be asked to complete a study center visit in place of a phone call visit. If a study center visit is requested, no additional assessments (other than collection of information on adverse events and concomitant medications) will be required (see [Section 11](#) – Study Schedule for details).

All females of childbearing potential must have a negative urine pregnancy test prior to enrolling in the study and must agree to use some form of birth control or agree to remain abstinent until

the study is completed. Since a pregnancy test will be performed at the final visit for SD-003, the results from that test can be utilized for entry into the SD-004 study. In addition, a urine pregnancy test will be performed every 6 months and at the final visit.

Safety assessments will include monitoring of tolerability, adverse events, and physical examinations.

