11. STUDY SCHEDULE

Procedure Visit	1 Screening/ Baseline	2 Week 2	3 Month 3	4 Month 6	5 Month 9	6 Month 12	7, 9, 11, and 13 Months 15, 21, 27, and 33	8, 10, 12, and 14 Months 18, 24, 30, and 36	15 (odd visits) Month 39 Phone Call	16 (even visits) Month 42 Site Visit	Alternate Phone Call and Site Visit until Final Study Visit/Early Termination ^a	Final Study Visit/Early Termination
Study Day (± 7 Days)	0	14	90	180	270	360	450, 630, 810, and 990	540, 720, 900, and 1080	1170	1260	-	-
Informed consent / assent signed	X											
Inclusion/Exclusion assessment	X											
Demographic, medical and medication history	X								X	X		X
Physical examination ^b	X											X
Height, weight, and temperature	X											X
Assess BSA ^c	X	X	X	X	X	X	X	X		X		X
Urine pregnancy test (females only) ^d	X			X		X		X		X		X
Dispense/re-dispense SD-101 cream ^e	X	X	X	X	X	X	X	X		X		X
Collect SD-101 cream for the purpose of drug accountability		X	X	X	X	X	X	X		X		X
Collect all SD-101 cream												X

Procedure Visit	1 Screening/ Baseline	2 Week 2	3 Month 3	4 Month 6	5 Month 9	6 Month 12	7, 9, 11, and 13 Months 15, 21, 27, and 33	8, 10, 12, and 14 Months 18, 24, 30, and 36	15 (odd visits) Month 39 Phone Call	16 (even visits) Month 42 Site Visit	Alternate Phone Call and Site Visit until Final Study Visit/Early Termination^a	Final Study Visit/Early Termination
Monitor adverse events	X	X	X	X	X	X	X	X	X	X		X
Monitor use of concomitant medications	X	X	X	X	X	X	X	X	X	X		X

- a. After completion of visit 14, the subject will return to the site once every 6 months (visits 16, 18, 20, etc.), with the intermittent 3 month visits conducted via telephone (visits 15, 17, 19, etc.). Telephone visits will include assessment of adverse events and concomitant medications only. At the Investigator's discretion, the subject may be asked to complete a study center visit in place of a phone call visit. If a study center visit is requested, no additional assessments (other than collection of information on adverse events and concomitant medications) will be required.
- b. A complete physical examination will be performed at the final visit. The physical examination performed at the final visit for SD-003 will be utilized as the baseline assessment for SD-004.
- c. The BSA assessment will be performed at visits 2 through 14 and at all subsequent scheduled study center visits. The BSA assessment performed at the final visit for SD-003 will be utilized as the baseline assessment for SD-004.

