11.2. Safety Assessments

The safety of SD-101 dermal cream (containing 6% allantoin) applied to the skin, will be assessed by monitoring tolerability at the application sites, adverse events, and physical examinations.

For timing of individual measurements, refer to [Section 11](#) - Study Schedule.

Physical Examination including height, weight, and temperature

Physical examinations will be done by a physician at the final study visit. The physical examination performed at the final visit for SD-003 will be utilized as the baseline assessment for SD-004. The following sites will be examined: head, eyes, ears, nose, throat, neck, chest, lungs, heart, abdomen, skin, and lymph nodes; and the following systems will be assessed: musculoskeletal and neurological. Weight, height, and temperature will be recorded.

Urinalysis

Urine pregnancy test for female subjects of child bearing potential (sensitivity at least 25 mIU/mL) will be performed at visits 4, 6, 8, 10, 12, 14, and at all subsequent study center visits. The urine pregnancy test performed at the final visit for SD-003 will be utilized for entry into SD-004.

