11.4. Definitions

Adverse Event (AE)

Any untoward medical occurrence in a patient, administered a medicinal product and which does not necessarily have to have a causal relationship with this treatment. An adverse event (AE) can therefore be any unfavorable and unintended sign (including an abnormal laboratory finding, for example), symptom, or disease temporally associated with the use of a medicinal product,

whether or not considered related to the medicinal product. AEs may include the onset of new illness and the exacerbation of pre-existing conditions.

The routine evolution of the disease condition under treatment according to the protocol will be evaluated as part of the disease symptoms assessments. Changes in the disease condition may not qualify as AEs. However, if there is a clinically relevant worsening of a sign or symptom of the condition under treatment and the outcome fulfills the definition of an AE, it must be reported as directed in the protocol.

Adverse Drug Reaction (ADR)

All events considered to be noxious and unintended responses to a medicinal product related to any dose should be considered adverse drug reactions, with the exception of skin site changes determined by the Investigator to be related to SD-101 dermal cream. These changes will be captured during the skin site evaluations (refer to [Section 9.3](#)). The phrase “responses to a medicinal product” means that a causal relationship between a medicinal product and an adverse event is at least a reasonable possibility, *i.e.*, the relationship cannot be ruled out.

Serious Adverse Event (SAE)

An adverse event that at any dose:

- Results in death
- Is life-threatening (*i.e.* the patient was at risk of death at the time of the event; it does not refer to an event which hypothetically might have caused death if it was more severe)
- Results in hospitalization or prolongation of existing hospitalization
- Results in persistent or significant disability/incapacity
- Is a congenital anomaly / birth defect
- Is considered to be an important medical event

Based upon medical and scientific judgment, important medical events that may not be immediately life-threatening, or result in death or hospitalization, but may jeopardize the patient or may require intervention to prevent one of the other outcomes listed in the definition above may be considered a serious adverse event.

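### The schedule omits the periodic physical examinations and the visit-by-visit skin examination that the protocol text promises, and the ADR exception relies on a skin evaluation that is nowhere described

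*Protocol*

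**What the plan says.** The protocol deals with safety assessment in several places.

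- **Synopsis, Safety Assessments:** safety rests on "monitoring tolerability at the application sites, adverse events, and periodic physical examinations".
- **Section 9.3:** "Safety assessments will include monitoring of tolerability, adverse events, and physical examinations". The same three measures appear, without the word periodic.
- **Section 8.4:** "Full skin examination will be performed at each scheduled study center visit". It then asks the investigator to consider discontinuing a subject for a new significant rash or for lesions worsening beyond the usual cycle.
- **Section 11, footnote b:** "A complete physical examination will be performed at the final visit", and "The physical examination performed at the final visit for SD-003 will be utilized as the baseline assessment for SD-004".
- **Section 11.2:** "Physical examinations will be done by a physician at the final study visit". For the timing of measurements it sends the reader to the Section 11 schedule ("For timing of individual measurements, refer to").
- **Section 11.4, Adverse Drug Reaction:** skin site changes that the investigator attributes to the cream are excepted from the ADR definition. The reason given is that "These changes will be captured during the skin site evaluations", with a reference to Section 9.3.

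**The concern.** The study exists to describe longer-term safety of a cream applied daily to the whole body, so local skin reactions are a central outcome. Three things do not fit together. The synopsis describes recurring physical examinations, while the operative sections give a single one after baseline. Section 8.4 requires a recurring skin examination that the schedule does not show. The ADR definition hands cream-related skin changes to an evaluation that the cited section does not contain.

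Sites tend to work from the schedule table. If the skin examination is not there and has no defined content, some sites may omit it and others may record it in different ways, and summaries of local tolerability over time would then not be comparable across sites or visits. The ADR exception adds to this. Section 11.4.2 frames the sponsor's expedited reporting around ADRs that are serious and unexpected, so whether a cream-related skin change counts as an ADR has a practical consequence.

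**Working it through.** The protocol gives no figure to reproduce, so the check sets the sections side by side and counts scheduled entries.

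**Step 1: number of site visits.** Visits 2 to 14 give 14 − 2 + 1 = 13 site visits after baseline. Visit 14 is on day 1080 and baseline is day 0, so they span 1080 − 0 = 1080 days (window ±7 days). Adding visit 16 (month 42) gives 14 site visits.

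**Step 2: entries at visits 2 to 14.**

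| Assessment | Protocol text | Schedule |
|---|---|---|
| Physical examination | Synopsis: periodic; footnote b and 11.2: final visit | 0 of 13 |
| Full skin examination | 8.4: 13 of 13 | no row, 0 of 13 |
| Application-site tolerability | Synopsis and 11.2: monitored, no timing stated | no row, 0 of 13 |
| Adverse events | 11.3: all visits | 13 of 13 |
| Lesional BSA | 9.2 and footnote c: every scheduled site visit | 13 of 13 |

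With visit 16 included, the physical examination stands at 0 of 14 and the skin or tolerability entry at 0 of 14. The reading of the physical examination row does not depend on the table layout, because footnote b and Section 11.2 say the same in words.

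**Step 3: interval between physical examinations.** There are two, at baseline and at exit, so the interval equals the subject's whole time on study. For a subject still on study at visit 14 that is about 1080 days or more. For one who leaves sooner it is shorter, because the schedule marks an early-termination examination.

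**Step 4: the cross-reference.** Section 11.4 points to Section 9.3 for skin site evaluations. Section 9.3 covers application of the cream, visit timing, BSA, telephone visits, pregnancy testing and a one-sentence list of safety measures. It describes no skin site evaluation. Section 11.2 describes the physical examination and the pregnancy test, but not how tolerability is assessed. Section 15.5 lists physical examinations among the entries required in the patient's file and names no skin examination or tolerability record.

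**Step 5: whether other data fill the gap.** Section 11.3 obtains adverse events from spontaneous report or general, non-leading questioning, which is not an examination. Section 11.4 adds that changes in the disease itself may not qualify as adverse events, and in a blistering disease a local reaction may be hard to tell from the disease. BSA (Section 9.2) scores the percentage of each region with blisters or lesions, and Section 11.1 lists it as efficacy. It measures extent and does not record irritation or rash as such.

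**The case against.** The strongest reply is that the gap lies in the drafting and not in the data. Several parts of it stand.

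- A reader might infer that two of the three named safety measures are not collected during treatment. The documents do not support that. Section 8.4 requires the skin examination without qualification, and body text binds sites even where the table has no row. What is missing is the schedule entry and a defined record.
- A reader might infer that there are no data on local tolerability or physical findings between baseline and exit. That also fails. Adverse events are collected at every visit and graded for severity and causality. Their definition covers any unfavorable sign or symptom, and clinically relevant worsening of the disease that meets the definition must be reported. The exception in Section 11.4 is written for ADRs and does not narrow the adverse event definition.
- A reader might infer that the skin-based discontinuation criteria in Section 8.4 have no recorded basis. Regional BSA at each scheduled site visit bears on lesion worsening, a new significant rash can be reported as an adverse event, and the primary reason for discontinuation is recorded.
- The eCRF is not shown, and Section 15.5 accepts data entered directly there as source data. A tolerability page may therefore exist.
- On physical examinations, the conflict turns on one word in the synopsis. Having only a final examination may be a deliberate choice, and nothing in the protocol shows that choice to be an error.

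The reply does not remove the missing schedule row, the cross-reference that leads to no described evaluation, or the disagreement over the word periodic.

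**Conclusion.** The point holds as an internal inconsistency in how the primary objective is measured, and it should be corrected. No physical examination is scheduled at any of the 13 site visits from 2 to 14, despite the synopsis. The skin examination required by Section 8.4 at all 13 appears at none of them in the schedule. The evaluation on which the ADR exception depends is not described where Section 11.4 says it is. Adverse event collection and BSA scoring reduce the consequence but do not replace a defined local tolerability assessment.

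This rests on the protocol text alone. It does not assume that sites omitted the examination or that the eCRF lacks a page for it. The protocol does not settle how often physical examinations are intended.

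**What to change.** 1. Add a row for full skin examination and application-site tolerability to the Section 11 schedule at every scheduled study center visit, as Section 8.4 already requires, and state that its findings are recorded.
2. Describe that assessment in Section 9.3 or 11.2, so that the reference in Section 11.4 leads to a real evaluation.
3. Reconcile the ADR exception in Section 11.4 with that assessment and with adverse event collection, so that treatment-related skin changes are captured.
4. Make the synopsis, Section 9.3, footnote b and Section 11.2 name the same visits for the physical examination. Which frequency is intended is for the sponsor to decide.

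The protocol carries over only the physical examination, BSA and pregnancy test from the final SD-003 visit, so the amendment should not assume that a tolerability baseline exists there.

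The cost is an amendment to a few sections, one schedule row and a place to record the findings. No visit is added, and the skin is already inspected for BSA at the same visits. Any extra cost for physical examinations depends on the frequency the sponsor confirms.

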3. LIST OF ABBREVIATIONS

ADR	Adverse Drug Reaction
AE	Adverse Event
BSA	Body Surface Area
BSAI	Body Surface Area Index
CRF	Case Report Form
EB	Epidermolysis Bullosa
EBS	Epidermolysis Bullosa Simplex
GCP	Good Clinical Practice
ICH	International Conference on Harmonization
IEC	Independent Ethics Committee
IRB	Institutional Review Board
ITT	Intent-to-treat
JEB-nH	Junctional non-Herlitz EB
MOA	Mechanism of Action
mITT	Modified-intent-to-treat
PP	Per Protocol
RDEB	Recessive Dystrophic Epidermolysis Bullosa
SAE	Serious Adverse Event
SUSAR	Suspected Unexpected Serious Adverse Reaction
WMA	World Medical Association

